## **MATERIALS AND METHODS**

### ***Study Population and Protocol***

This was a single-center, prospective, assessor-blinded, noninferiority, randomized controlled study conducted at a tertiary referral center (Incheon St. Mary's Hospital, Incheon, Korea). Individuals who underwent colonoscopy with or without esophagogastroduodenoscopy (EGD) for various indications were eligible for inclusion. Study subjects were enrolled between November 2017 and February 2018. Individuals who met all of the following criteria were included: (1) age 40–75 years; (2) American Society of Anesthesiologists (ASA) class I or II; (3) outpatients; and (4) no previous history of bowel resection or gastrectomy. Exclusion criteria were as follows: (1) cancellation, (2) violation of protocol for bowel preparation, such as subjects in the SDD group ingesting a purgative the previous day or as an SPD; or subjects in the SPD group ingesting a purgative the previous day or as an SDD. After informed consent was obtained, study subjects were randomly assigned to the SDD or SPD group. Randomization was performed using a block size of four, stratified by colonoscopy time (morning vs afternoon) and sex, using a computer-generated randomization list.

The protocol for bowel preparation is shown in Figure 1. Subjects underwent bowel preparation at home. Study subjects were encouraged to finish 2 L PEG within 1 h. If ingestion was difficult, 2 L PEG was consumed within 1.5 h. Hence, 2 to 3 h were required to fully ingest the 4 L PEG. Individuals in the SDD group ingested PEG on the day of the colonoscopy. For those who underwent morning colonoscopy, ingestion of 4 L PEG was started at 5 a.m. Individuals who were scheduled to undergo afternoon colonoscopy were instructed to take 2 L PEG starting at 7 a.m., then after a 2-h break, the remaining 2 L PEG was ingested starting at 10 a.m. Individuals in the SPD were instructed to begin ingesting 2 L

PEG at 9 p.m., 1 day before the colonoscopy. The remaining 2 L PEG was ingested from 7 a.m. for morning colonoscopy or from 10 a.m. for afternoon colonoscopy. We encouraged the participants to ingest additional water until their bowel effluent was clear. Consumption of fibers and seeds was restricted for 2 days before colonoscopy. Soft food was allowed for dinner the day before colonoscopy. Colonoscopy was performed between 10 a.m. and 5 p.m. (morning colonoscopy 10 a.m.–12 p.m.; afternoon colonoscopy 1:30 p.m.–5 p.m.) by three board-certified colonoscopists with experience of more than 2000 cases. The colonoscopists were blinded to the bowel cleansing regimen. This study was approved by the Institutional Review Board of Incheon St. Mary's Hospital and registered at ClinicalTrials.gov (NCT03315949).

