### ***Statistical Analysis***

We assumed a bowel cleansing success rate for SPD of 85% and set the inferior margin at 10%. With 80% power and a type I error of 0.05, the required sample size for each group was calculated to be 158. A total of 176 subjects in each group was required, considering a 10% drop-out rate. Continuous variables are expressed as mean  $\pm$  standard deviation. Categorical variables are expressed as number and percent. The demographic characteristics, bowel cleansing efficacy, safety profile, tolerability, bowel movement kinetics, and results of colonoscopy were compared between the two groups. For this analysis, we used Student's *t* test for continuous variables, and the chi-square or Fisher's exact test for categorical variables. A *p*-value  $<0.05$  was considered significant. The safety analysis of safety and

tolerability included all subjects except those who were excluded for cancellation or protocol violation. Per-protocol (PP) analysis was used for the patients who completed colonoscopy. Bowel cleansing efficacy and bowel movement kinetics were investigated in the PP analysis. All statistical analyses were conducted using SAS software (9.0; SAS Institute, Cary, NC, USA).

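### A single fixed block size of four within strata would let a fully informed observer deduce about a third of allocations; varying, undisclosed block sizes would nearly remove this at little cost

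*Combined protocol and SAP*

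**What the plan says.** Study Population and Protocol describes a "single-center, prospective, assessor-blinded, noninferiority, randomized controlled study". On allocation it says: "Randomization was performed using a block size of four, stratified by colonoscopy time (morning vs afternoon) and sex", and adds that this was done "using a computer-generated randomization list". Assignment comes after consent. Crossing the two stratification factors gives 2 × 2 = 4 strata, and both factors are known when a subject is enrolled.

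The regimens differ in when the purgative is taken. For a morning colonoscopy, SDD starts at 5 a.m. on the day and SPD starts at 9 p.m. the evening before. Intake is self-managed: "Subjects underwent bowel preparation at home". On masking, the section says "The colonoscopists were blinded to the bowel cleansing regimen" and names no other role as blinded.

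Statistical Analysis gives the planned size: "A total of 176 subjects in each group was required, considering a 10% drop-out rate". No allocation ratio is stated; equal groups imply 1:1.

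The text does not say who held the list, how each assignment was released, or whether those enrolling subjects knew the block size or could see earlier assignments.

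**The concern.** A fixed small block becomes more predictable as it fills. Once one arm has used its two places, the rest of the block is determined. Stratification does not prevent this, because the stratum of the next subject is known. At a single center all earlier assignments are made in one place, and whoever gives the intake times must know the arm.

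Blinding the colonoscopists protects the scoring of bowel cleansing. It does not protect the steps before assignment: whom to approach, when to approach them, and whether to book a morning or an afternoon slot. Obtaining consent before assignment does not fully close the gap, because a foreseeable next assignment can influence who is approached at all. If subjects likely to prepare well were steered to one arm, the difference in success rates would shift. Here that difference is judged against a 10-point noninferiority margin.

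**Working it through.** **The plan's own figure.** The inputs from Statistical Analysis are 85% success in SPD, a margin of 10 points, type I error 0.05, 80% power and 10% drop-out. Equal true success in SDD is an assumption, because the plan does not state it. With one-sided 0.05:

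n per group = (1.645 + 0.842)² × 2 × 0.85 × 0.15 / 0.10² ≈ 157.7, rounded up to 158.

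Allowing for drop-out, 158 / 0.90 = 175.6, rounded up to 176. The total is 2 × 176 = 352. Both stated figures reproduce, so 352 is the denominator below. The plan gives no predictability figure to compare with.

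**Allocations known with certainty, fixed block of four.** There are C(4,2) = 6 equally likely 2:2 blocks.

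- Positions 1 and 2 are never determined.
- Position 3 is determined in 2 of 6 blocks (AABB and BBAA).
- Position 4 is always determined.

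Expected share = (0 + 0 + 1/3 + 1) / 4 = 8/24 = 1/3. Applied to 352 subjects, 352 / 3 ≈ 117. At least one allocation per complete block is determined, so the minimum with all blocks complete is 352 / 4 = 88.

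**Best-guess accuracy, fixed block of four.** The observer names the arm with more places left and tosses a coin when they are equal. The chance of being right is 1/2, 2/3, 2/3 and 1 at positions 1 to 4. The mean is 17/24 = 70.8%, against 50% with no information.

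**Alternatives.** For a fixed block of 2m with known boundaries, the certain share is 1/(m + 1), and best-guess accuracy is (m + 2^(2m−1)/C(2m,m) − 1/2)/(2m). For randomly varying sizes the figures come from simulation: 88 subjects per stratum (352 / 4, an assumption of equal strata), sizes drawn with equal probability, 1,500 runs. The simulated observer knows which sizes are possible but not which were drawn.

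| Block sizes | Known with certainty | Best guess correct |
|---|---|---|
| 4, fixed (plan) | 33.3% | 70.8% |
| 6, fixed | 25% | 68.3% |
| 8, fixed | 20% | 66.6% |
| 4 and 6, varying | about 5.5% | about 69% |
| 2, 4 and 6, varying | about 4.1% | about 70% |
| 4, 6 and 8, varying | about 2.4% | about 68% |

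With sizes 4, 6 and 8, the expected number of certain allocations falls from about 117 to about 0.024 × 352 ≈ 8.

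**Cost in balance.** The largest imbalance in an unfinished block is half its size: 2 for a block of four and 4 for a block of eight. Over four strata the extreme total is 4 × 2 = 8 against 4 × 4 = 16, and it requires every stratum to stop at its worst point in the same direction.

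**The case against.** The strongest objection is that one third describes an ideal observer. To reach it, enrolling staff must know or infer the block size, see every earlier assignment, and keep track of four interleaved strata. The documents establish none of this. They do not say who enrolled, assigned or instructed subjects, or whether these were the same people. A block size in a methods section does not show that recruiters knew it. This stands: one third is the expected share for a fully informed observer and a ceiling for anyone who knows less.

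A second objection is that the remedy barely changes best-guess accuracy, and steering can work on a good guess. This also stands. The advantage over a coin toss falls only from 20.8 to about 18 percentage points. The gain is in certainty, which makes deliberate steering reliable.

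Third, blocks of four within strata are a legitimate choice for balance, and blinded colonoscopists score the primary endpoint. Both are true, but neither bears on foreknowledge at enrolment.

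A reader might go further and infer that removing cancellations and protocol violators after randomization would hide any such bias. The documents do not support that. Steering acts before assignment, so those exclusions are a separate matter. Statistical Analysis also plans a comparison of demographic characteristics between the groups, which is a partial check, although unmeasured traits could escape it.

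**Conclusion.** The point holds as a minor design improvement. One fixed block size of four, in four strata known at enrolment, at one center and with no concealment described, leaves up to one third of allocations (about 117 of 352 in expectation) open to deduction by someone who knows the block size and follows each stratum. The figure assumes 1:1 blocks, complete tracking and the planned total; incomplete final blocks change it slightly.

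A reader might infer that a third of allocations actually were predictable to the enrolling staff, or that the comparison is biased. The documents show neither. They are silent on what staff knew, and they contain nothing from which the size or direction of a bias could be computed.

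**What to change.** Generate the list with randomly varying block sizes, for example 4, 6 and 8, within the same four strata, and withhold the sizes from enrolling staff and from any text they hold. The cost is one parameter in the program that produces the list, a sentence in the protocol, and the larger possible end-of-stratum imbalance shown above, which is small beside 176 per group.

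The text describes enrolment as finished, so the change applies to a list still to be generated, such as a repeat of this design. For this trial, a sentence stating who held the list, how assignments were released and whether the block size was withheld would let readers judge how far the ceiling applies.

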### ***Bowel Cleansing Efficacy, Bowel Movement Kinetics, and Colonoscopy Results***

The primary endpoint of this study was the bowel cleansing efficacy assessed by the Boston bowel preparation scale (BBPS). The BBPS score is the sum of three segmental scores (range 0–9). Each segment is graded on a 4-point scale: 0, inadequate; 1, poor; 2, good; and 3, excellent. The rates of cleansing success, defined as all segments  $\geq 2$  and total BBPS score, were compared between groups. The bowel cleansing efficacy was also assessed by the Aronchick scale, which has scores of excellent, good, fair, poor, and very poor; details of the Aronchick scale are described elsewhere.

Bowel movement kinetics included the number of defecations, the start and finish time of bowel preparation, and the last defecation time. The amount of PEG and additional water ingested were recorded.

The results of the colonoscopy were analyzed. The cecal intubation time, colonoscopy withdrawal time, polyp detection rate (PDR), ADR, and the number of adenomas per patient

were recorded. For those who underwent EGD, fluid in the stomach was suctioned and its volume was measured.

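### Same-day dosing follows a different schedule for morning and afternoon colonoscopy, yet no result by colonoscopy time is planned

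*Combined protocol and SAP*

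**What the plan says.** Under Study Population and Protocol, randomisation uses blocks of four and is "stratified by colonoscopy time (morning vs afternoon) and sex". The same section sets these start times:

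| | First 2 L | Second 2 L |
|---|---|---|
| SDD, morning | 5 a.m. | straight on; the text describes no break |
| SPD, morning | 9 p.m. the day before | 7 a.m. |
| SDD, afternoon | 7 a.m. | 10 a.m. |
| SPD, afternoon | 9 p.m. the day before | 10 a.m. |

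The sources are "For those who underwent morning colonoscopy, ingestion of 4 L PEG was started at 5 a.m" for SDD in the morning, "then after a 2-h break, the remaining 2 L PEG was ingested starting at 10 a.m" for SDD in the afternoon, and "The remaining 2 L PEG was ingested from 7 a.m. for morning colonoscopy or from 10 a.m. for afternoon colonoscopy" for SPD. Clinic hours are "morning colonoscopy 10 a.m.–12 p.m.; afternoon colonoscopy 1:30 p.m.–5 p.m".

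Under Bowel Cleansing Efficacy, Bowel Movement Kinetics, and Colonoscopy Results, the cleansing success rate "and total BBPS score, were compared between groups". Statistical Analysis names the t test, chi-square test and Fisher's exact test for comparing the two groups. Neither section describes an estimate by colonoscopy time, an interaction, or an analysis stratified by the randomisation factors.

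**The concern.** The label SDD covers two schedules, and the contrast with SPD is not the same in both. In the afternoon the second 2 L has the same stated start in both groups, so only the timing of the first 2 L differs. In the morning the first 2 L differs, and the second may differ too. The design treats colonoscopy time as important enough to stratify on, but the analysis then ignores it.

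A reader who wants to know about one same-day schedule would have only the pooled result. If SDD performed worse on one schedule and not on the other, nothing in the planned output would show it.

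**Working it through.** **Timing.** A 2 L portion takes 1 h, or up to 1.5 h ("If ingestion was difficult, 2 L PEG was consumed within 1.5 h"). If the morning SDD group takes no break, its second 2 L starts at 05:00 + 1 to 1.5 h = 06:00 to 06:30, which is 0.5 to 1 h before the 07:00 start in SPD. This point is conditional: "The protocol for bowel preparation is shown in Figure 1", that figure was not available, and a break of 30 to 60 minutes there would remove the difference. Two differences by time do not depend on the figure. SDD starts at 5 a.m. in one stratum and 7 a.m. in the other. The first doses of the two groups are 8 h apart in the morning (21:00 to 05:00) and 10 h apart in the afternoon (21:00 to 07:00).

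**The plan's sample size.** Inputs from Statistical Analysis: 85% success (taken as equal in both groups), 10-point margin, 80% power, type I error 0.05. With n = (z + 0.8416)² × 2 × 0.85 × 0.15 / 0.10²:

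- one-sided 0.05 (z = 1.6449): 157.7, so 158, and 158 / 0.9 = 175.6, so 176, both as stated;
- one-sided 0.025 (z = 1.9600): 200.1, so 201.

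The plan gives no decision rule. Its sample size implies a lower 90% limit compared with -10 points, and that rule is used below. The trial is sized for the pooled comparison only.

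**Afternoon share.** No counts by time are given, so 50, 64 and 75% are assumed. The middle value is the ratio of clinic hours, 3.5 / 5.5 = 0.636, and is not an enrolment figure. The corresponding morning/afternoon numbers per group are 79/79, 57/101 and 40/118.

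**What the pooled difference can conceal.** With no afternoon deficit, the true pooled difference equals the morning share times the morning deficit. It stays inside -10 points until the morning deficit exceeds 10 / morning share: 10 / 0.50 = 20, 10 / 0.364 = about 28, and 10 / 0.25 = 40 points.

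**How often pooled noninferiority is declared.** The normal approximation is Φ((0.10 + Δ) / SE − 1.6449), where Δ is the pooled difference. For a 15-point morning deficit at a 50% share:

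- Δ = −0.15 × 0.50 = −0.075, so SDD success is 0.775;
- SE = √[(0.85 × 0.15 + 0.775 × 0.225) / 158] = 0.0437;
- the probability is Φ(0.572 − 1.645) = 0.14.

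Simulation of 400,000 trials with Wald limits gives:

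| Morning deficit, none in the afternoon | 50% afternoon | 64% | 75% |
|---|---|---|---|
| 10 points | 32% | 46% | 57% |
| 15 points | 14% | 29% | 44% |
| 20 points | 5% | 16% | 32% |
| 15 points, lower 95% limit instead | 8% | 19% | 31% |

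For the 15-point deficit the true pooled difference is -7.5, -5.4 or -3.8 points, inside the margin, so the pooled conclusion is not false.

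**What reporting by time would show.** The 95% half-width is 1.96 × √(2 × 0.85 × 0.15 / n per group); for the interaction the two stratum variances are added. At 79 per group: 1.96 × √(0.255 / 79) = 0.111.

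| | 50% afternoon | 64% | 75% |
|---|---|---|---|
| Half-width, morning (points) | 11 | 13 | 16 |
| Half-width, afternoon | 11 | 10 | 9 |
| Half-width, interaction | 16 | 16 | 18 |
| Half-width, pooled | 8 | 8 | 8 |
| Morning estimate below -10, 15-point deficit* | 31% | 46% | 46% |
| Morning estimate below -10, no deficit* | 1% | 3% | 4% |
| Interaction power, 15-point deficit* | 33% | 32% | 28% |
| Morning lower 95% limit at or below -10, no deficit* | 48% | 59% | 69% |

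*Among trials that declare pooled noninferiority.

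**What stratifying the pooled test would add.** A stratified Miettinen-Nurminen test over four strata (28/29/50/51 per group, 300,000 trials) gains 0, 0.1 or 0.8 points of power when morning and afternoon success differ by 0, 10 or 20 points. With the 15-point morning deficit it still declares noninferiority in 14, 28 or 43% of trials. Stratification alone therefore does not expose the deficit.

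**The case against.** The strongest case against acting is that nothing here is wrong. The question posed is overall noninferiority; stratified randomisation balances colonoscopy time between groups; and the plan claims nothing for either schedule alone. SPD's second dose also moves with the appointment, so each SDD schedule is compared with its own SPD counterpart. The morning-only deficits are hypothetical, and at an even split the pooled test passes in only 14% of trials at 15 points and 5% at 20. The remedy is imprecise: morning half-widths exceed the 10-point margin, interaction power is about 30%, and in more than half of the passing trials the morning estimate would not fall below -10. Enrolment ran to February 2018, so prespecification may no longer be possible.

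Most of this stands, and it sets the weight of the point. The pooled inference is sound, the deficits are illustrative, and results by time can only be descriptive. It does not answer the omission, which depends on no assumed deficit: the schedules differ, time is a stratum, and no output separates them. Nor are imprecise estimates uninformative, given 31 to 46% against 1 to 4% for a morning estimate below -10. The negligible gain from stratifying is accepted.

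One further objection is that 7 a.m. plus 1.5 h of drinking plus a 2-h break gives 10:30, so the afternoon second doses need not coincide. That holds for slow drinkers who take the full break, but the stated start is 10 a.m. in both groups.

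**Conclusion.** The concern holds, as an improvement to the analysis and not as an error in the primary inference. The plan stratifies on colonoscopy time, gives SDD a different schedule in each stratum, and provides no result by time. Figure 1 shows the preparation schedule, so its absence does not affect this finding.

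Under the stated assumptions, a 15-point morning-only deficit would pass the pooled test in 14 to 44% of trials (8 to 31% with a lower 95% limit). The size depends on the unknown morning share and on the deficit chosen. The point deserves action because both factors are already recorded and the reporting is nearly free. Confidence is medium, because no data by time are given and the noninferiority rule had to be inferred from the sample size.

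**What to change.** **Main change.** In Statistical Analysis, add the SDD-SPD difference in cleansing success with its 95% confidence interval for morning and for afternoon colonoscopy, and the regimen-by-time interaction estimate with its interval. Label these descriptive, and post hoc if outcomes have already been examined. State that each stratum compares an SDD schedule with the SPD schedule for the same appointment time.

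**Minor change.** Estimate the primary risk difference stratified by colonoscopy time and sex, with a stratified score-type interval (for example stratified Miettinen-Nurminen) compared with -10 points. This brings the analysis into line with the randomisation, at a gain of under 1 point of power in the cases examined.

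**Cost.** A few sentences and a few extra estimates, with no new data. The drawback is imprecision. Even with no true deficit, the morning lower 95% limit reaches -10 in 48 to 69% of trials that declare pooled noninferiority. The text should therefore say that neither a wide morning interval nor a nonsignificant interaction is evidence for or against a deficit.

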### ***Bowel Cleansing Efficacy, Bowel Movement Kinetics, and Colonoscopy Results***

The primary endpoint of this study was the bowel cleansing efficacy assessed by the Boston bowel preparation scale (BBPS). The BBPS score is the sum of three segmental scores (range 0–9). Each segment is graded on a 4-point scale: 0, inadequate; 1, poor; 2, good; and 3, excellent. The rates of cleansing success, defined as all segments  $\geq 2$  and total BBPS score, were compared between groups. The bowel cleansing efficacy was also assessed by the Aronchick scale, which has scores of excellent, good, fair, poor, and very poor; details of the Aronchick scale are described elsewhere.

Bowel movement kinetics included the number of defecations, the start and finish time of bowel preparation, and the last defecation time. The amount of PEG and additional water ingested were recorded.

The results of the colonoscopy were analyzed. The cecal intubation time, colonoscopy withdrawal time, polyp detection rate (PDR), ADR, and the number of adenomas per patient

were recorded. For those who underwent EGD, fluid in the stomach was suctioned and its volume was measured.

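### Two BBPS measures share the primary endpoint, the margin belongs to the success rate only, and the stated tests use the margin for neither

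*Combined protocol and SAP*

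**What the plan says.** The Study Population and Protocol section describes the trial as a "single-center, prospective, assessor-blinded, noninferiority, randomized controlled study".

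The section on bowel cleansing efficacy, bowel movement kinetics and colonoscopy results defines the endpoint: "The primary endpoint of this study was the bowel cleansing efficacy assessed by the Boston bowel preparation scale (BBPS"). Two measures on that scale follow in one sentence. It opens "The rates of cleansing success, defined as all segments" (at least 2) and ends "and total BBPS score, were compared between groups". Neither measure is called the primary variable, and neither is called secondary.

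The Statistical Analysis section gives the design assumptions: "We assumed a bowel cleansing success rate for SPD of 85% and set the inferior margin at 10" (per cent), then "With 80% power and a type I error of 0.05, the required sample size for each group was calculated to be 158". It allows for drop-out: "A total of 176 subjects in each group was required, considering a 10% drop-out rate". It has no margin, standard deviation or threshold for the total score. For the analysis it names Student's t test for continuous variables and chi-square or Fisher's exact test for categorical ones, with p<0.05 as the criterion. It describes no confidence interval, no test against the margin, and no rule for the case where the two BBPS measures point in different directions.

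**The concern.** A noninferiority trial needs one variable, one margin and one decision rule, linked in writing. Here the endpoint section names a concept (efficacy on the BBPS) with two measures under it, the margin appears in another section for one of them, and the tests described do not use it.

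The two measures can disagree. Segment scores of 1, 3 and 3 total 7 out of 9, yet the subject is a cleansing failure because one segment is below 2. A group comparison of total scores can therefore look reassuring when the success rate does not.

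At stake is what the report may claim. The only written criterion is p<0.05 for a difference. If that test is nonsignificant, on the rate or on the score, the result could be described as comparable cleansing under the primary endpoint. A nonsignificant difference is not evidence that the deficit is smaller than 10 points.

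**Working it through.** **Inputs.** From the Statistical Analysis section: SPD success rate 0.85, margin 0.10 (read as 10 percentage points), power 80%, type I error 0.05, drop-out 10%. Assumed, because not stated: the SDD rate equals the SPD rate, groups are of equal size, and the type I error is one-sided.

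**1. Which variable does the sample size belong to?** For noninferiority on a proportion with equal true rates,

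n per group = 2p(1−p)(z₀.₉₅ + z₀.₈₀)² / margin²

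= 2 × 0.85 × 0.15 × (1.6449 + 0.8416)² / 0.10² = 157.7, so 158.

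With drop-out: 158 / 0.90 = 175.6, so 176.

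Both stated figures reproduce. The other settings tried do not give 158: noninferiority at one-sided 0.025 gives 201, and superiority of 85% over 75% gives 250 (two-sided 0.05) or 197 (one-sided 0.05). The sample size is therefore that of a noninferiority test on the success rate at one-sided 0.05.

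**2. Does the sample size say anything about the total score?** Only if a standard deviation and a margin are supplied, and the documents give neither. With 158 per group, one-sided 0.05, 80% power and no true difference, the smallest margin that can be tested is SD × √(2/158) × (1.6449 + 0.8416). An assumed SD of 1.0 gives 0.28 points, and an assumed SD of 2.0 gives 0.56. Nothing in the plan selects a value in that range.

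**3. What does a difference test say about the success rate at the margin?** Take the true rates as 0.85 (SPD) and 0.75 (SDD), with 158 per group and a two-sided 0.05 test (the sidedness of the test is an assumption).

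- Standard error under no difference, pooled rate 0.80: √(2 × 0.80 × 0.20 / 158) = 0.0450.
- Standard error at the true rates: √((0.85 × 0.15 + 0.75 × 0.25) / 158) = 0.0447.
- Probability of significance: Φ((0.10 − 1.96 × 0.0450) / 0.0447) = 0.604.
- Probability of a nonsignificant result: 1 − 0.604 = 0.396.

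If nonsignificance were read as noninferiority, a regimen exactly 10 points worse would pass about 40% of the time. The design allows 5%.

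**4. A single hypothetical result.** Suppose 134 of 158 succeed on SPD (84.8%) and 123 of 158 on SDD (77.8%).

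- Difference, SDD minus SPD: −7.0 points.
- Standard error: √((0.848 × 0.152 + 0.778 × 0.222) / 158) = 0.0437.
- Uncorrected chi-square: 2.52, p = 0.11, nonsignificant.
- One-sided 95% lower limit: −0.070 − 1.6449 × 0.0437 = −0.141.

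The limit lies beyond −10 points, so noninferiority is not shown, although the planned test finds no significant difference.

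**The case against.** The strongest reply is that the deciding variable can be identified. The assumed rate, the margin and the sample size all refer to the success rate, and 158 and 176 reproduce from it exactly. That two measures were compared does not make both of them primary: the Statistical Analysis section uses similar language for demographics, safety and kinetics. All of this stands, and it means the gap is in the written rule. It does not show that the trial was designed without a primary variable.

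A reader might go further and infer that noninferiority can be won formally on either measure, with an inflated type I error. The documents do not support that. A score without a margin cannot carry a formal noninferiority conclusion, and no section says that a favourable result on either measure suffices. Any either-measure error rate, or rate of disagreement on noninferiority, needs a total-score margin that the plan does not contain, so none is given here.

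It is also fair to say that the difference test is not a weakness of the total score alone. The success rate is assigned to a chi-square or Fisher's test with the same limitation. This is correct, and it is why naming the variable without stating the method would leave the problem in place.

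Finally, the punctuation allows a reading in which the total score is part of the success definition. That reading is weak, because no cut-off for the score is given, but it is a further reason to rewrite the sentence.

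**Conclusion.** The point holds in a limited form. The success rate is the implied primary variable, but the plan does not say so, places the total score beside it under the same endpoint, and describes only difference tests that ignore the 10-point margin. The documents do not show an intention to choose the more favourable measure. They leave room for a nonsignificant difference on either measure to be presented as support for noninferiority.

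The size can be given for the success rate: about a 40% chance of a nonsignificant result when SDD is exactly 10 points worse, against the planned 5% error. This assumes true rates of 85% and 75%, 158 analysed per group, a two-sided 0.05 chi-square test, and that nonsignificance is taken as noninferiority, which the plan does not state but does not rule out. No size can be given for the total score. The one-sided 0.05 level is inferred from the reproduced sample size. Whether that level is appropriate is a separate question.

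**What to change.** In the endpoint section, name the cleansing success rate (all three segments at least 2) as the sole primary variable. List the total BBPS score as secondary, reported as a between-group difference with a confidence interval and not used for the noninferiority claim. Reword the sentence so that the total score cannot be read as part of the success definition.

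In the Statistical Analysis section, state the rule: noninferiority is concluded if the lower one-sided 95% confidence limit for the SDD minus SPD difference in success rate (equivalently, the lower end of the two-sided 90% interval) lies above −10 percentage points. Name the interval method. State that a nonsignificant t, chi-square or Fisher's test is not evidence of noninferiority.

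The cost is a few sentences. The sample size is unchanged at 158 per group, or 176 with drop-out, because it already rests on this variable and this level. The downside is that the total score can no longer support the main claim.
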